7.1.5 Follow up for Participants who Discontinued Study Intervention

Discontinuation from receipt of Sing2016 M2SR H3N2 vaccine or placebo does not mean discontinuation from the study, and remaining study procedures may be completed as indicated by the study protocol. Participants who receive a single dose of vaccine or placebo, but joined the study in Cohorts 4, 5, 6, or 7, and were thereby assigned to receive 2 doses of vaccine or placebo, will still be offered the seasonal licensed influenza vaccine (IIV4) at the time indicated in the protocol. Such participants will be followed on the schedule of activities in the same manner as participants in Cohorts 1, 2, and 3 (who were assigned to receive only a single dose of vaccine or placebo). If a clinically significant finding is identified (including, but not limited to changes from baseline) after enrollment, the investigator or qualified designee will determine if any change in participant management is needed. Any new clinically relevant finding after study product administration will be reported as an adverse event (AE).

7.2 Participant Withdrawal from the Study and Replacement

Parents/guardians of participants are free to withdraw their child from participation in the study at any time upon request. An investigator may discontinue or withdraw a participant from the study for the following reasons:

1. Study non-compliance that in the opinion of the investigator poses an increased risk or compromises the validity of the data
2. If any clinical adverse event (AE), laboratory abnormality, or other medical condition or situation occurs such that continued participation in the study would not be in the best interest of the participant, in the opinion of the investigator
3. Medical disease or condition, or new clinical finding(s) for which continued participation, in the opinion of the investigator, might compromise the safety of the participant, interfere with the participant's successful completion of this study, or interfere with the evaluation of responses
4. Participant lost to follow-up

If the parent/guardian of the participant agrees, every attempt will be made to follow all AEs through resolution.

Participants whose parents withdraw them, or who are withdrawn from this study, or are lost to follow-up after signing the informed consent form (ICF) but prior to administration of study product may be replaced, at the discretion of the sponsor.

Given it is crucial to have an adequate pre-vaccination blood specimen from all children who enroll, participants from whom pre-vaccination blood is not successfully collected are not eligible to participate in the study.

The reason for participant discontinuation or withdrawal from the study will be recorded on the appropriate Case Report Form (CRF).

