5.6.2 Retention

Once a child has received study product, study staff will make every effort to retain him or her in follow-up for the protocol-specified duration of follow-up, i.e., through the influenza season as defined in the protocol, thereby minimizing potential biases associated with loss to follow-up.

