5.5. Missing Data and Outliers

No imputation is planned for missing data.

Any data point that appears to be erroneous or inexplicable based on the observed data distribution and the statistical team's understanding of the analysis variables will be investigated as a possible outlier. If data points are identified as outliers, sensitivity analyses may be performed to examine the impact of including or excluding the outliers. Any substantive differences in these analyses will be reported.

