8.1.1.3. Unsolicited Adverse Events

When calculating the incidence of adverse events on the participant-level, each participant will only be counted once at the maximum value of the respective variable (e.g., maximum severity, maximum relatedness, etc.) and any repetitions of adverse events within a participant will be ignored. All adverse events reported will be included in the summaries and analyses.

The number and percentage of participants reporting at least one unsolicited adverse event will be summarized by MedDRA SOC and PT. Denominators for percentages are the number of participants who received the vaccination being summarized where applicable.

The following summaries of AEs will be provided:

- Incidence of the following by severity and relationship to study product
 - Non-serious unsolicited AEs in the 28 days following each study vaccination and across study vaccinations ([Table 40](#) through [Table 50](#))
 - AESIs ([Table 51](#) through [Table 58](#))
 - SAEs ([Table 59](#) through [Table 66](#))
 - NOCMCs ([Table 67](#) through [Table 74](#))
- Bar chart of the incidence of the following by severity of:
 - Non-serious unsolicited AEs in the 28 days following each study vaccination and across study vaccinations ([Figure 34](#) through [Figure 38](#))
 - AESIs ([Figure 39](#) through [Figure 41](#))
 - SAEs ([Figure 42](#) through [Figure 44](#))
 - NOCMCs ([Figure 45](#) through [Figure 47](#))
- Total frequency by severity, relationship to study product, and resolution of:
 - Non-serious unsolicited AEs in the 28 days following each study vaccination and across study vaccinations ([Table 75](#) through [Table 85](#))
 - AESIs ([Table 86](#) through [Table 93](#))
 - SAEs ([Table 94](#) through [Table 101](#))
 - NOCMCs ([Table 102](#) through [Table 109](#))

- Bar chart of frequency by severity of
 - Non-serious unsolicited AEs following each study vaccination and across study vaccinations ([Figure 48](#) through [Figure 52](#))
 - AESIs ([Figure 53](#) through [Figure 55](#))
 - SAEs ([Figure 56](#) through [Figure 58](#)),
 - NOCMCs ([Figure 59](#) through [Figure 61](#))

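### Protocol 7.2 lets an investigator withdraw an already dosed child without continuing SAE, AESI and NOCMC ascertainment to April, while the SAP keeps that child in the denominator

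*Protocol*

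**What the plan says.** Protocol 7.2 opens its list with: "An investigator may discontinue or withdraw a participant from the study for the following reasons". Reason 1 is non-compliance that raises risk or undermines the data. Reason 2 begins "If any clinical adverse event (AE), laboratory abnormality, or other medical condition or situation occurs" and applies where staying in would not serve the child's best interest. Reason 3 covers a disease, condition or new finding that might compromise safety, hinder completion of the study, "or interfere with the evaluation of responses". Replacement is allowed only for children who leave before receiving product. For those withdrawn, and only if the parent or guardian agrees, "every attempt will be made to follow all AEs through resolution".

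Two neighbouring sections concern retention. Protocol 7.1.5 says that stopping "vaccine or placebo does not mean discontinuation from the study". Protocol 5.6.2 says: "Once a child has received study product, study staff will make every effort to retain him or her in follow-up".

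On analysis, the AESI, SAE and NOCMC endpoints run from first vaccination to the final visit in April of the next calendar year (SAP 3.2 and 4.6.1). For unsolicited events, including these three types, SAP 8.1.1.3 says: "Denominators for percentages are the number of participants who received the vaccination being summarized where applicable". SAP 5.5 adds: "No imputation is planned for missing data". The mITT population needs at least one post-baseline sample (SAP 5.3.4) or result (Protocol 9.3). The first is due 28 days after the last study vaccination.

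**The concern.** Cohorts 1 to 3 receive all investigational product on Day 1. What remains is follow-up contact, IIV4 and two sampling visits. For those children, withdrawal from the study after dosing mainly stops data collection, including collection for three primary endpoints. The protocol synopsis puts participation at up to 14 months, so an early withdrawal could leave most of that time unobserved.

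The children concerned are not a random subset. Reasons 2 and 3 select on an adverse event, a condition or a new finding after dosing. If later events are more likely in such children, the long-term percentages would be too low.

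The evaluation-of-responses ground is the weakest part of the rule, because it is scientific rather than protective. SAP 5.3.5 already deals with compromised responses at data level: the child stays in mITT and the affected data leave only the per-protocol set. Section 7.2 allows the same worry to end participation before the data exist.

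**Working it through.** **Is ascertainment restored anywhere else?**
- Protocol 7.1.5 covers stopping product, not leaving the study.
- Protocol 5.6.2 is a general retention effort and sets no procedure after withdrawal.
- Protocol 8.4.6 follows SAEs already recorded to resolution.
- Protocol 8.4.10.1 asks for reports of suspected related SAEs that an investigator learns of after study completion. It covers neither NOCMCs, AESIs nor unrelated SAEs.
- Protocol 8.4.13, by contrast, asks a pregnant participant for permission to keep following her. Section 7.2 has no such provision.

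No section continues the search for new SAEs, AESIs or NOCMCs.

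**What is counted?**
- The adverse event that led to withdrawal is counted. SAP Table 24 has a row for events leading to early termination, and the event enters the AESI, SAE or NOCMC tables if it qualifies.
- Solicited events are divided by children with data (SAP 8.1.1.2), so missing diaries are not read as absence of symptoms.
- Later events of the three long-term types are divided by all who were vaccinated, with nothing imputed.

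**Reproducing the plan's precision figures.** For 0 events in n children, the upper exact 95% limit is U(n) = 1 − 0.025^(1/n). This gives U(15) = 21.8%, U(30) = 11.6% and U(90) = 4.0%, as in Protocol Table 6 (SAP Table 4).

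**Effect of w withdrawals with no events seen.** The plan's limit is U(N). Counting only children followed throughout gives U(N − w). The documents give no withdrawal rate, so w is assumed.

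| N | w | U(N) | U(N − w) | Difference (points) |
|---|---|---|---|---|
| 15 | 1 | 21.8% | 23.2% | 1.4 |
| 15 | 2 | 21.8% | 24.7% | 2.9 |
| 15 | 3 | 21.8% | 26.5% | 4.7 |
| 30 | 1 | 11.6% | 11.9% | 0.3 |
| 30 | 2 | 11.6% | 12.3% | 0.7 |
| 30 | 3 | 11.6% | 12.8% | 1.2 |
| 90 | 9 | 4.0% | 4.5% | 0.5 |
| 90 | 18 | 4.0% | 5.0% | 1.0 |

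U(N − w) gives a withdrawn child no credit for time already observed. These differences are therefore at the high end for withdrawal unrelated to later events.

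**If the withdrawn child later has an unseen event.** This needs two assumptions: one withdrawal in the group, and one later event in that child. At N=15 the report would read 0/15 (0 to 21.8%) instead of 1/15 = 6.7% (0.2 to 31.9%). At N=30 it would read 0/30 (0 to 11.6%) instead of 1/30 = 3.3% (0.1 to 17.2%). All intervals are exact Clopper-Pearson.

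**mITT.** A child withdrawn before Visit 4 (Cohorts 1 to 3) or Visit 4C (Cohort 4) has no scheduled post-baseline sample and leaves mITT. A child withdrawn later stays in, with only later samples missing.

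**The case against.** The best defence is that the clause is permissive and limited. Reason 2 carries a best-interest test, and reason 1 requires added risk or damage to data validity. Related bronchospasm, generalized urticaria within 72 hours and related SAEs fall under the individual halting criteria in Protocol 7.1.3. Those stop product only, and 7.1.5 then keeps the child in the study. An all-dosed denominator for SAEs is conventional. Early terminations are visible: SAP Table 8 shows by group how many completed safety follow-up to the end of the study, and Listing 2 gives dates and reasons. After 28 days wheeze surveillance relies on parents in any case. All of this stands, and it limits the point.

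It does not close the gap. Showing how many children left does not recover their later events, and the incidence tables do not carry the number followed.

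A reader might go further and infer four things that the documents do not support:
- **The withdrawn child counts as wholly event-free.** The event causing withdrawal is counted and listed; only later or other events are taken as absent.
- **Withdrawal removes immunogenicity data.** Nothing deletes data already collected, and mITT membership is lost only before the first post-baseline sample.
- **7.2 contradicts 7.1.5 and 5.6.2.** The first concerns product and the second is an effort commitment; both can hold alongside 7.2.
- **The safety percentages are biased, and differently by arm.** Investigators are blinded. A difference between arms would need an imbalance in adverse events and withdrawal because of it, and neither is documented.

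**Conclusion.** The point holds in limited form. Section 7.2 permits study withdrawal of a dosed child under reasons 1 to 3, including on an evaluability ground, and does not keep that child under ascertainment for new SAEs, AESIs and NOCMCs. SAP 8.1.1.3 then treats the unobserved time as free of such events. Withdrawal before the first post-baseline sample also costs mITT membership on a post-randomisation ground.

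The numerical effect of one withdrawal unrelated to later events is small: 1.4 points on the zero-event upper limit at N=15 and 0.3 at N=30. It matters more if withdrawal is related to later events, since one unseen event is the difference between 0/15 and 1/15. How often the clause is used is unknown, so no bias can be estimated from the documents. The reason to act is that three primary endpoints depend on this follow-up and the repair is inexpensive.

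**What to change.** Leave the investigator's authority on best-interest and safety grounds unchanged. Then:

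1. State in Protocol 7.2 that any dosed child withdrawn under reasons 1 to 3 will, with parent or guardian agreement, remain in SAE, AESI and NOCMC follow-up by phone or record review to the April visit, and in sampling where feasible.
2. Remove interference with response evaluation as a ground for ending study participation after dosing. Handle such cases through the per-protocol data exclusions in SAP 5.3.5, with the child kept in mITT.
3. In the SAP, report SAE, AESI and NOCMC percentages beside the number followed to April in each group. Table 8 already produces that count.

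The cost is about a paragraph of protocol text, one extra figure per group in the tables, and slightly more site work per affected child. The SAP describes study conduct in the past tense. If follow-up has closed, only item 3 can still be applied to this trial.

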7.3 Lost to Follow-Up

A participant will be considered lost to follow-up if he or she fails to return for scheduled visits and is unable to be contacted by the study site staff.

8. STUDY ASSESSMENTS AND PROCEDURES

8.1 Screening Procedures (Day -28 to -1, or Day 1):

Screening may occur on Days -28 to -1 or may occur on the day of vaccination, Day 1. During the screening visit, after the study is described to the parent/guardian and child, when appropriate, the parent/guardian will provide written permission and the participant, when appropriate, will provide assent, prior to any study-related procedure. Eligibility will be determined.

Study staff will collect demographic information, medical history, concomitant medications, and either perform or review the physical examination (that is, the physical exam may be performed by the participant's clinical provider, who is not a member of the study team or by a qualified study team member). No safety laboratory tests will be collected. Blood for immune response and nasal washes will be collected at the vaccination visit, prior to vaccination, to establish a baseline. Female participants of childbearing potential will have a urine pregnancy test performed and recorded as negative within the 24 hours prior to vaccination. This test will not be done at a screening visit if the visit is not within 24 hours prior to vaccination. Blood will be collected for immunological assays and a nasal wash will be collected for immunological assays on Day 1, prior to vaccination.

8.1.1 Procedures to be Followed in the Event of Abnormal Laboratory Test Values or Abnormal Clinical Findings

If a physiologic parameter, e.g., body temperature, is outside of the protocol-specified range, then the measurement may be repeated once if, in the judgment of the investigator, the abnormality is unlikely to represent the true body temperature. A physiologic parameter may also be repeated if there is a technical problem with the measurement caused by a malfunctioning or inappropriate measuring device, or for any other reason that the investigator believes has led to a spurious result.

A participant may be re-screened if there is a transient disease status (e.g., participant complained of a “cold or fever” and met a temporary delaying enrollment criterion of acute illness or fever) or if a protocol eligibility criterion that is not met at the initial time of screening, will be met by rescreening at a later date (e.g., a medication taken within exclusionary window at the time of first screening that would not be within exclusionary window at a later rescreen).

No participant may be screened more than twice due to a screening failure result as defined above.

Parents of participants will be provided the results of any abnormal clinical laboratory results (such as a respiratory viral panel result) and will be referred to their primary healthcare provider. Research laboratory results will not routinely be provided to the parent of the participant.

8.2 Efficacy / Immunogenicity Assessments

There are no efficacy evaluations in this study. Immunological evaluations include humoral immune responses, cellular immune responses, and mucosal immune responses following one or two doses of Sing2016 M2SR H3N2 vaccine or placebo. These evaluations also include

immunological evaluations following seasonal influenza vaccine provided to participants after having received 1 or 2 doses of Sing2016 M2SR H3N2 vaccine or placebo.

8.2.1 Humoral Immune Evaluations After Sing2016 M2SR H3N2 Vaccine

Humoral immune evaluations will include HAI, neutralization, anti-HA, and anti-NA antibodies against the homologous vaccine (Sing2016M2SR H3N2) antigens. Responses to heterologous antigens may also be assessed. Analysis of extra-neutralizing function of antibodies to homologous and heterologous strains may also be performed on an exploratory basis according to positive responses obtained for assays described above and specimen availability.

8.2.2 Cellular Immune Evaluations After Sing2016 M2SR H3N2 Vaccine

Cellular immune evaluations will include T-cell responses and antigen-binding B cells to homologous antigen epitopes and may include assessment of responses to heterologous antigen epitopes. Also, these evaluations might include B memory assessment of responses by ELISpot if enough cells are available.

8.2.3 Mucosal Immune Evaluations After Sing2016 M2SR H3N2 Vaccine

Mucosal immune evaluations will include measurement of secretory IgA from nasal wash specimens (sIgA) against homologous vaccine antigens. Additional measurements may include HAI, neutralization, as well as anti-HA and anti-NA IgG and/or IgM antibodies and analysis of extra neutralizing antibody function on an exploratory basis according to specimen availability.

8.2.4 Immune Evaluations After Seasonal Influenza Vaccine (IIV4)

Humoral immune evaluations after seasonal influenza vaccine will include serum HAI and neutralization as well as mucosal secretory IgA to vaccine-containing strains. Additional measurements may include anti-HA, anti-NA antibodies and extra-neutralizing antibody function according to responses obtained in assays described above and specimen availability.

Cellular response analysis after seasonal influenza vaccine will include T-cell responses and antigen-binding B cells and may include responses to heterologous strains; analysis of B memory responses by ELISpot may be included according to cell availability.

8.3 Safety and Other Assessments

Safety will be assessed by evaluations of the frequency and severity of solicited AEs (reactogenicity), unsolicited non-serious AEs, AESIs, NOCMCs, and SAEs.

8.3.1 Solicited AEs (Reactogenicity)

Solicited AEs can be divided into immediate post-vaccination events, local reactogenicity events, and systemic reactogenicity events. The immediate events will be recorded by the study staff in the 20 minutes after each vaccination. All solicited events with corresponding grades as described in [Section 8.4.3](#) will be evaluated. These severity grades include mild, moderate, or severe.

Local and systemic reactogenicity events will then be recorded by the parent/guardian daily from Day 1 to Day 8 after the first vaccine or placebo and the 7 days following the second vaccination for participants in Cohorts 4, 5, 6, and 7 with the use of a memory aid. The local events are those

in and around the nares, where the vaccine is administered. Local and systemic events are described in [Table 4](#), below.

8.3.2 Unsolicited Non-Serious AEs

We will record unsolicited non-serious AEs, both medically attended and not, from the time of vaccination on Day 1 until 28 days after the last vaccination (Day 29 for Cohorts 1, 2, and 3 and approximately Day 57 for Cohorts 4, 5, 6, and 7).

8.3.2.1 Suspected Unexpected Serious Adverse Reactions (SUSAR)

A SUSAR is any SAE where a causal relationship with the study product is at least a reasonable possibility but is not listed in the Investigator Brochure, Package Insert, and/or Summary of Product Characteristics.

8.3.3 Adverse Events of Special Interest (AESIs).

Given that there is a theoretical possibility that intranasal influenza vaccines will lead to increased rates of acute onset wheeze and that these events may not always be captured by the other safety assessments, these events will be deemed AESIs. AESIs will be collected from the time of the first study vaccination on Day 1 until individual participant study completion, but with special emphasis paid to the 28 days following each intranasal vaccination. Details on the evaluation of this AESI are found in [Appendix B](#) – Evaluation Criteria for Acute Wheezing.

8.3.4 New Onset Chronic Medical Conditions (NOCMCs).

NOCMCs are defined as any new ICD-10 diagnosis that is applied to the participant during the duration of the study, after receipt of the study agent, that is expected to continue for at least 3 months and requires continued health care intervention. These events will be collected from the time of the first study vaccination on Day 1 until the end of the study period (the final visit done in April of the calendar year following enrollment).

8.3.5 Serious Adverse Events (SAEs).

SAEs will also be collected from the time of the first study vaccination on Day 1 until the end of the study period (the final visit done in April of the calendar year following enrollment).

8.3.6 Procedures to be Followed in the Event of Abnormal Laboratory Test Values or Abnormal Clinical Findings

The site PI or appropriate sub-investigator is responsible for recording all AE/SAEs that are observed or reported during this trial, when they occur in the timeframes described, regardless of relationship to study product. AE/SAEs, abnormal laboratory test values, or abnormal clinical findings will be collected, assessed, documented, reported, and followed appropriately.

8.4 Adverse Events and Serious Adverse Events

8.4.1 Definition of Adverse Events (AE)

Adverse event means any untoward medical occurrence associated with the use of an intervention in humans, whether considered intervention-related (21 CFR 312.32 (a)). An AE can therefore be any unfavorable and unintended sign (including an abnormal laboratory finding), symptom, or disease temporally associated with the use of medicinal (investigational)

product. Any medical condition that is present at the time that the participant is screened will be considered as baseline and not reported as an AE. However, if the severity or frequency of any pre-existing medical condition increases, it will be recorded as an AE.

Adverse events can be further divided into solicited adverse events and unsolicited adverse events. Solicited adverse events are those for which the study team will specifically query the participant or parent/guardian whether they occurred. Unsolicited adverse events are those events that the participant or parent/guardian reports occurring without being queried about the specific event.

All AEs will be assessed for severity and relationship to study intervention (see [section 8.3.3](#)). All AEs, solicited and unsolicited, will be captured on the appropriate data collection form. Information to be collected for AEs includes event description, date of onset, assessment of severity, relationship to study product and alternate etiology (assessed only by those with the training and authority to make a diagnosis and listed on the Form FDA 1572 as an investigator), date of resolution, seriousness, and outcome. AEs occurring during the trial collection and reporting period will be documented appropriately regardless of relationship.

AEs will be followed through resolution.

